1) Abstract of the study

STUDY OBJECTIVES: This is a randomized, double blind, placebo controlled, tolerability-based, dose escalating inpatient trial to determine the effect and duration of multiple doses of clavulanic acid (CLAV) on glutamate (Glu) levels, using neuroimaging, in an addiction related brain area (the anterior cingulate cortex [ACC]) in subjects with cocaine use disorder (CocUD) who have achieved one week of abstinence.

Primary Objective: The primary objective of this study is to determine whether once-aday repeated CLAV 500 (or higher, 750/1000 mg, see dose escalation in study design) in patients with CocUD in early remission produces reductions in brain Glu levels at day 10 compared to baseline, as assessed by Magnetic Resonance Spectroscopy (MRS) in the anterior cingulate (ACC).

Secondary Objectives: A) To assess changes in craving-associated neurocircuitry (frontal-striatal-thalamic connectivity) using resting state functional Magnetic Resonance Imaging (rs-fMRI). Subjects with CocUD will have decreased functional connectivity between nodes within the frontal-striatal-thalamic network (Wang et al. 2018) involving mesocorticolimbic circuit nodes (Gu et al. 2010). After repeated CLAV, we expect that the fronto-striatal-thalamic within network functional connectivity will increase. We also will determine whether improved network connectivity as associated with decreased craving as determined by the Cocaine Craving Questionnaire (CCQ) and a Visual Analog Scale (VAS). B) To evaluate whether CLAV 500, 750, 1000 mg a day given repeatedly for 10 days (to steady state, rationale below) and then stopped, is associated with a sustained reduction in brain glutamate concentration measured in the ACC one day after cessation of CLAV dosing (to determine the duration of CLAV action on glutamate after last dose and to determine the feasibility of once daily CLAV dosing). C) To evaluate whether 10 days of treatment with CLAV is associated with increases in brain glutamine concentration as assessed by MRS in the ACC. D) To assess CLAV 500, 750, and 1000 mg/day safety and tolerability by: a) the rates of occurrence of adverse events; b) changes in vital signs; c) EKG parameters; and d) laboratory study changes.

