Exploratory Objectives: A) To evaluate whether repeated CLAV treatment 500, 750, 1000 mg/day suppresses cue-induced limbic fMRI activation. B) To evaluate whether CLAV treatment 500, 750, 1000 mg/day for 10 days is associated with subjective effects measured by Visual Analog Scales (VAS), the Profile of Mood States (POMS). C) To evaluate whether CLAV treatment 500, 750,1000 mg/day for 10 days is associated with cognitive and executive function deficits as assessed by the Cambridge cognition survey batteries. D) To evaluate whether Adverse Childhood Experiences (ACEs) are associated with increased outcomes of subjective reports of mood and craving.

STUDY ENDPOINTS:

Primary Endpoint: Change in brain glutamate concentration in the ACC at Day 10 compared with baseline. **Secondary Endpoints**:

- A) Brain connectivity change in the ACC on resting state fMRI. CCQ and VAS for craving.
- B) Change in brain glutamate concentration in the ACC at Day 11 compared with Day 10.
- C) Change in brain glutamine concentration in the ACC at Day 10 compared with baseline.
- D) Safety and tolerance as assessed by the rates of occurrence of adverse events, changes in vital signs, Columbia Suicide Severity Rating Scale (C-SSRS), EKG parameters and laboratory studies compared with baseline.

Exploratory Endpoints:

- A) Suppression of cocaine cue-induced limbic activation during imaging task.
- B) Subjective effects will be compared before and after CLAV 500, 750,1000 mg/day for 10 days using the following instruments: Visual Analog Scales (VAS), Profile of Mood States (POMS).
- C) Scores from the Cambridge Cognition Cognitive battery at multiple timepoints compared with baseline.
- D) Relationship between scores from the Adverse Childhood Experiences (ACE) scale, POMS, and VAS.

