STUDY DESIGN: This is a randomized, double-blind, placebo-controlled, parallel group inpatient study of clavulanic acid, 500, 750,1000 mg given orally once a day for 10 days. Subjects are adults (18-70) in early remission who are seeking treatment for cocaine use disorder. In rodents, CLAV 1 mg/kg is associated with a decrease in cocaine intake after 5-7 days, which is then maintained and can be considered steady state. A conservative estimate for steady state in humans is CLAV administration for 10 days. For those subjects who can tolerate 500 mg/day for 3 days (or matched placebo), there will be a forced dose escalation to 750 mg/day for 3 days. For those subjects who cannot tolerate an increased dose will return to the last tolerable dose for the remainder of the study.

Structural MRI, functional MRI, and MRS will be done before study drug administration at baseline, after 3 days of study drug administration (prior to 750mg dose escalation), after 6 days of study drug administration (prior to the 1000mg dose escalation) on the last day of study drug administration (day 10), and one day after the last dose of study drug (day 11). The final MR scan session will be used to gather information on the duration of CLAV's effect on anterior cingulate cortex glutamate concentration after cessation of CLAV dosing. At the time of each scan, safety of the subject to complete the scan will be re-assessed. Subjective and cognitive assessments will be administered daily in the inpatient setting. Assessments of adverse effects, blood pressure and pulse will also be performed daily.

STUDY DURATION: Study duration is 3 outpatient visits (screening and follow up) and 11 inpatient days. There will be 5 MRI/MRS studies during the inpatient portion of the study. The pre-intake screening will last up to 30 days. After participants are discharged

from the inpatient portion of the study, they will be asked to return for the follow up visit 5-8 days after discharge. The visit will include an assessment of adverse events to determine withdrawal symptoms. All adverse events will be followed by study staff until resolution.

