CLAV is preferable to CTX for testing the hypothesis that GLT-1 activation can prevent COC self-administration and other glutamate-associated toxicities. CTX has 3 drawbacks as a drug for human use. First, it must be given parenterally. Second, it is an antibiotic, so its use can give rise to drug resistant bacteria. Third, CTX displays poor blood brain barrier (BBB) penetrability, which requires the use of high doses for CNS efficacy (typically 200 mg/kg/ day in rodents). These doses equate to about 13 g/day in a human, approximately 5 times greater than CTX doses used for meningitis. Compared with CTX, CLAV displays greater BBB permeability with mean CLAV ratios, cerebrospinal fluid to plasma, of ~23% in neurosurgical patients with normal BBB (Nakagawa et al. 1994). Chronic cocaine use has been associated with a proinflammatory state, so the BBB permeability of CLAV may be increased in chronic users (Fiala et al. 1998). CLAV has negligible antibiotic activity (Saudagar, Survase, and Singhal 2008), so there is very low risk of developing drug resistant strains. CLAV is an oral drug, which is a practical delivery system for an inpatient study. We hypothesize that CLAV, an existing drug that is brain penetrable, safe and orally active offers a realistic candidate for cocaine pharmacotherapy. Repeated CTX administration produced a dose-dependent reduction in glutamate levels in that persist for up to 20 days following discontinuation of drug exposure (Rasmussen, Unterwald, and Rawls 2011). The prolonged reduction in glutamate levels after CTX discontinuation suggest that CTX's effect on glutamate is not a PK-mediated mechanism, since the half-life of CTX is short (~ 6 hours). We plan to investigate whether CLAV, given repeatedly for 10 days, is also associated with reduced glutamate levels after discontinuation of drug exposure with an MRS scan 24 hours after the last CLAV dose.

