Exploratory objectives are to: A) To evaluate whether repeated CLAV treatment 500, 750, 1000 mg/day suppresses cue-induced limbic fMRI activation. B) To evaluate whether CLAV treatment 500, 750, 1000 mg/day for 10 days is associated with subjective effects measured by the Visual Analog Scales (VAS), the Profile of Mood States (POMS). C) To evaluate whether CLAV treatment 500, 750, 1000 mg/day for 10 days is associated with cognitive and executive function deficits as assessed by the Cambridge cognition survey batteries.

Data Statistical Analysis Plan

Demographic and Baseline Comparability Analyses

Demographic variables will be summarized both separately and together for all male and female patients.

Primary Analyses:

ACC glutamate concentrations at days 0, 10 and 11 are the primary assessment variables. Glu level differences assessed by MRS in the ACC after 10 days of CLAV dosing 500, 750, 1000 mg/day will be compared with baseline and presented. The MRS raw data will be taken directly from the scanner and the software package, TARQUIN (http://tarquin.sourceforge.net/) will be used to measure the quantities of metabolites present in the AC. The software recognizes scanning parameters from the data and

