Assessment of ACC Glu level one day after the last CLAV dose will be compared with the level on the last day of CLAV dosing. Resting state fMRI data preprocessing and analyses will be performed using statistical parametric mapping (SPM) (http://www.fil.ion.ucl.ac.uk/spm) based custom batch scripts (Wang et al. 2015, Wang et al. 2017, Li, Kadivar, et al. 2012, Li, Zhu, et al. 2012). Seed region-based functional connectivity (SRFC) will be calculated as the correlation coefficient (CC) of the resting state fMRI signal from a seed and any voxel in the rest of the brain. A Priori seeds will be defined in anterior cingulate (ACC), amygdala, ventral striatum (VS), insula, ventromedial prefrontal cortex (VMPFC), posterior cingulate cortex (PCC), and lateral prefrontal cortex (PFC). These regions are known to be affected by cocaine addiction, suggesting that their connections to other regions may be impaired as shown in (Gu et al. 2010) and may be predictive of relapse (Adinoff et al. 2015). ACC Regions of Interest (ROI) in the Montreal Neurological Institute (MNI) standard brain will be defined based on the previous SRFC work in cocaine addiction (Gu et al. 2010). Other seeds will be based on suprathreshold clusters from the literature or manually defined using the SPM Pickatlas utility (Maldjian et al. 2003). The individual subjects' FC maps will be first registered into the image space of the T1-weighted structural MRI and then registered into the MNI standard brain using SPM (version 12). The registration transform will be derived from the projection from the T1-weighted structural MRI to the MNI space.

There will be an assessment of glutamate level one day after the last dose compared with the last day of dosing after last dose.

Assessments for glutamine will be similar to those for glutamate.

Adverse events will be tabulated overall as well as by study group, and by body system and organ class if desired. In addition, all adverse events (AE's) noted during the study will be listed. The listings will include each occurrence of the AE, when it was reported, the severity and the duration. Adverse event data will be compiled for CLAV and placebo and presented as summary statistics. Subjective craving effects of CLAV from the visual analog scale and CCQ will be evaluated similarly as described in the above for glutamate.

Exploratory Analyses:

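### Secondary objective B asks whether the glutamate reduction is still present at Day 11, but its endpoint compares Day 11 only with Day 10, which measures offset and not whether a reduction remains

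*Combined protocol and SAP*

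**What the plan says.** Objective B appears in the Abstract, in section 5 (Objectives) and under Secondary Outcome Measures. It asks whether CLAV, given for 10 days and then stopped, "is associated with a sustained reduction in brain glutamate concentration measured in the ACC one day after cessation of CLAV dosing". Section 6 (Background) gives the Day 11 scan the same purpose: to see whether CLAV "is also associated with reduced glutamate levels after discontinuation of drug exposure with an MRS scan 24 hours after the last CLAV dose". The Abstract and Secondary Outcome Measures add two aims, duration of action after the last dose and the feasibility of once-daily dosing. The Study Design text says "The final MR scan session will be used to gather information on the duration of" the drug's effect.

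Endpoint B is given in the Abstract, in section 5 and in section e) Study Endpoints as "Change in brain glutamate concentration in the ACC at Day 11 compared with Day 10". Secondary Analyses states the same contrast twice. First, the glutamate level "one day after the last CLAV dose will be compared with the level on the last day of CLAV dosing"; later, "There will be an assessment of glutamate level one day after the last dose compared with the last day of dosing after last dose". It names no test for this comparison.

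Primary Analyses is less clear. It says "ACC glutamate concentrations at days 0, 10 and 11 are the primary assessment variables", but the only comparison with baseline that it spells out is of differences "after 10 days of CLAV dosing 500, 750, 1000 mg/day will be compared with baseline and presented". A later sentence there compares glutamate before and after study drug without naming a day. The between-arm test is a one-sided Mann-Whitney-Wilcoxon test at 0.05.

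**The concern.** A statement that a reduction persists needs a pre-drug reference. Endpoint B uses the last dosing day instead. It therefore answers how much of the effect went away overnight, and leaves open whether glutamate is below its starting level at Day 11.

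Objective B is the trial's evidence on duration of action and on whether once-daily dosing is feasible, and the plan says its results will guide the next step of the project. As written, a flat Day 10 to Day 11 change could be taken as persistence when it is only a failure to detect loss. If Day 11 versus baseline is not specified beforehand, whether and how to use it would be decided after the data are seen.

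**Working it through.** **Expected values.** Write the CLAV-minus-placebo difference in change from baseline as d10 at Day 10 and d11 at Day 11. Endpoint B estimates d11 − d10.

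| Scenario | d10 | d11 | d11 − d10 |
|---|---|---|---|
| Inert drug | 0 | 0 | 0 |
| Full effect, sustained | −1.01 | −1.01 | 0 |
| Half lost overnight | −1.01 | −0.505 | +0.505 |
| All lost overnight | −1.01 | 0 | +1.01 |

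The first two rows share an endpoint B value of zero. They differ only in d11, which endpoint B does not report. This step needs no assumed figure.

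**Inputs for size.** From Rationale for Sample Size: means 8.39 and 7.38 (difference 1.01), SD 0.76, 9 CLAV and 3 placebo. The documents give no SD for Day 11 minus Day 10 or for Day 11 minus baseline. I assume 0.76 for every contrast and show a range from 0.38 to 1.07. The upper end is 0.76 × √2, which applies if 0.76 is the SD of a single scan.

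**The plan's own figure.** There are 220 orderings of 3 versus 9. Rejecting at U ≤ 5 has exact alpha 16/220 = 0.073 and gives 63.4% power for 1.01, which reproduces the stated 63% (stated actual alpha 0.075). Rejecting at U ≤ 4 has exact alpha 11/220 = 0.050 and gives 55.0%. The rank-test results below use U ≤ 4.

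**Simulation.** Baseline, Day 10 and Day 11 scans have independent errors with per-scan SD equal to the change SD divided by √2, with 400,000 trials per scenario. Because the plan names no test for Day 11 versus Day 10, three are shown: the between-arm one-sided rank test, and two-sided and one-sided paired t-tests within CLAV.

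If the drug is inert, at SD 0.76, a significant Day 10 reduction followed by no significant rise occurs in 4.0% of all trials (rank) or 4.7% (two-sided paired).

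The next table is conditional on a significant Day 10 result, except for its first and last rows, which cover all trials.

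| | SD 0.38 | SD 0.76 | SD 1.07 |
|---|---|---|---|
| Day 10 significant, true effect 1.01 (all trials) | 96.6% | 55.1% | 35.1% |
| All lost, no significant rise: rank | 3.0% | 32.5% | 46.9% |
| All lost: paired, two-sided | 0.0% | 4.4% | 22.1% |
| All lost: paired, one-sided | 0.0% | 1.5% | 11.5% |
| Half lost, no significant rise: rank | 43.6% | 68.2% | 72.6% |
| Half lost: paired, two-sided | 6.1% | 52.0% | 68.5% |
| Half lost: paired, one-sided | 2.2% | 36.6% | 54.5% |
| Day 11 vs baseline significant (rank): sustained | 97.0% | 67.7% | 53.1% |
| Day 11 vs baseline significant: half lost | 56.4% | 31.9% | 27.4% |
| Day 11 vs baseline significant: all lost | 5.1% | 7.9% | 10.2% |
| Sustained, significant at both days (all trials) | 93.6% | 37.3% | 18.6% |

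**Precision (95% CI half-widths, t-based).**
- Between arms at Day 11: t(10) × SD × √(1/3 + 1/9) = 2.228 × 0.76 × 0.667 = 1.13 (0.56 to 1.59 over the SD range).
- Day 11 minus Day 10 within CLAV: t(8) × SD / √9 = 2.306 × 0.76 / 3 = 0.58 (0.29 to 0.82).

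**The case against.** The best defence is that persistence presupposes a reduction. The primary endpoint tests for one, and endpoint B then asks whether it holds overnight. The two add up to Day 11 minus baseline, so nothing is lost. Day 10 is also a sensible reference for duration: that scan follows a dose, the Day 11 scan does not, and the half-life is at most 2 hours. The plan already promises summaries by arm and, where appropriate, confidence intervals on the endpoints. It never says that a non-significant rise will be read as persistence, and it calls its analyses mostly descriptive. Finally, the added between-arm contrast is less precise than the within-CLAV one and brings another unadjusted one-sided test.

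Much of this stands. Day 11 versus Day 10 serves the duration aim and should stay. The inert-drug case is largely removed once Day 10 is positive. With a paired test at SD 0.76, a complete loss is rarely missed, so the concern is mainly partial loss. The miss rates depend on a test the plan does not name.

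It does not close the gap. The promised intervals attach to the endpoints as defined, and Day 11 versus baseline is not one of them. That it can be derived does not make it specified. The finding that Day 11 versus baseline is still significant in 32% of trials after half loss is no error either, because half the reduction is then present; the offset estimate shows how much was lost.

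**Conclusion.** The concern holds. The mismatch between objective B and endpoint B follows from the wording alone. The plan nowhere expressly states a Day 11 versus baseline contrast; listing Day 11 among the assessment variables and an undated before-and-after comparison leave it ambiguous.

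The size rests on an effect of 1.01, an SD of 0.76 for every contrast and independent scan errors. The consequence is limited: one secondary objective in a largely hypothesis-generating trial, with all the data already collected and the primary analysis untouched. It should be corrected because correction is cheap.

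**What to change.** 1. In endpoint B (Abstract, section 5 and section e), add the baseline-to-Day 11 change in ACC glutamate, CLAV versus placebo. Analyse it with the primary's one-sided Mann-Whitney-Wilcoxon test, with an estimate and confidence interval. Interpret it as persistence only if Day 10 shows a reduction.
2. Keep Day 11 minus Day 10 as a descriptive offset estimate by arm with a confidence interval. State that a non-significant value is not evidence of persistence.
3. Amend the two Day 11 sentences in Secondary Analyses to match, and name the days covered by the before-and-after comparison in Primary Analyses.
4. State that with 9 versus 3 the Day 11 estimate is imprecise, so a non-significant Day 11 result does not show loss of effect.

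The cost is a few clauses, with no added scan or subject. The drawback is low precision. At SD 0.76 the between-arm half-width of 1.13 exceeds the assumed effect of 1.01, and a truly sustained effect would be significant at both days in only about 37% of trials.

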Common adverse events for Augmentin include: diarrhea (14.5%), vaginal mycosis (3.3%), nausea (2.1%) and loose stools (1.6%). As a beta lactam drug, CLAV has a risk of allergic reactions for those with known penicillin allergy. The risk of hepatitis for Augmentin® is estimated at between 1/10,000 to 1/100,000, with an increased risk for older males (Gresser 2001). Hepatotoxicity associated with amoxicillin/ CLAV is generally self-limited with cessation of medication and generally associated with complete recovery (Saudagar, Survase, and Singhal 2008, Gresser 2001, Larrey et al. 1992). Single dose studies with sodium clavulanate were performed at both 750 mg (5 subjects) and 1000 mg (2 subjects) (FDA 05/09/1988). After 750 mg, 4 of 5 subjects had symptoms, although they were mild in 3 and consisted of "slight sleepiness, borborygmi and a heavy feeling in the epigastrium. The fourth subject had marked malaise, indigestion, and slight headache between 1/2-2 hours after dosing and later epigastric discomfort and diarrhea which persisted for several hours." The medical literature supports the hypothesis that CLAV at doses up to 500 mg/day and CLAV given as a chronic medication is generally safe and well tolerated. Combined amoxicillin clavulanate (CLAV 250 mg a day) has been given to men to treat actinomycetoma for a mean of 9.6 months with no reported side effects (Bonifaz et al. 2007). Combined meropenem/clavulanate (CLAV 375 mg a day) has been given to 6 patients with drugresistant tuberculosis for up to 36 weeks with no reported side effects (Payen et al. 2012). Timentin® is an intravenous combination of ticarcillin and CLAV, with 100 mg of CLAV in a 3.1 gram infusion of Timentin. In a retrospective study of 127 pediatric cystic

fibrosis patients who received Timentin, they received a mean of 450 mg CLAV /day +/-227 mg/day for a mean duration of 13.5 days (Zobell et al. 2010). No adverse effects on laboratory measures, including liver function tests, were found. While there is substantial clinical experience with Augmentin to treat infections, there is no published data on either CLAV or Augmentin in cocaine dependent adults. In our inpatient study of 3 doses of CLAV in combination with cocaine 40 mg, 10 subjects have received single doses of CLAV 500 mg, and 5 subjects have received single doses of CLAV 750 mg in combination with cocaine. All doses have been reasonably well tolerated without serious adverse effects.

This is an inpatient study to be conducted on a medical unit at the Episcopal Hospital campus of the Temple University Health System (T-EH). In the event that space is unavailable on C6 for medical reasons, Temple University Hospital Main (TUH-Main) and Jeanes Hospital medical floors which can provide nursing staff who are not currently assigned Covid patients will serve as back up sites. T-EH,TUH-Main and Jeanes are fully equipped hospitals, with 24-hour Emergency Departments. The Hospitalist teams for Episcopal Hospital, TUH Main, and Jeanes Hospital will be fully briefed on the study. The Chief Medical officer of Episcopal Hospital, [name], Executive Vice President and Chief Medical officer of TUH-Main [name], nursing management, nurses on all shifts of the medical unit, pharmacy and security will be briefed on the study and will be updated at least every six (6) months and more frequently if needed.

Interested candidates between the ages of 18 and 70 who have been determined to be cocaine dependent subjects with 7+ days of abstinence, or who express interest in remaining abstinent from cocaine, will meet with the investigators/study team by phone or in person and receive an explanation of the study purpose and requirements at the inpatient sites. If still interested after receiving an explanation of the study, the candidate will complete a prescreen questionnaire. Interested candidates who complete the prescreen are given an ID and have their data from the prescreen questionnaire stored in REDCap. Participant names are not stored in REDCap and are kept separately in a password protected excel file on a secure Temple server. If a candidate expresses interest in the study but has already completed a prescreen questionnaire, the study team will review their prior prescreen to determine whether they were excluded based on criteria that may have changed since they last contact the study team. If a participant may still be eligible, the study team will ask the candidate if they can update their information to determine whether they may be eligible for the study.

Participants who are potentially eligible based on the prescreen questionnaire will be given an opportunity to review, inquire about, and sign the study informed consent form approved by the Temple University Institutional Review Board (IRB). Screening of

subjects to establish eligibility will occur over the phone or video (for screening part 1) or in person (part 1 and 2) at the inpatient unit to establish cocaine use, appropriate age, and no excluded medical or psychiatric conditions.

Temple University Main Campus – Scans

MRI scans will be conducted with the Siemens MAGNETOM Prisma 3-Tesla wholebody MRI scanner in Weiss Hall of the main campus of Temple University. It supports a collection of structural MRI, MRS, BOLD fMRI, ASL, perfusion MRI and DTI sequences. This instrument provides the strongest commercially available gradient field (80mT/m) in combination with the fastest available gradient switching rate (200mT/m/s). The magnet's coil uses an ultra-high-performance cooling and force-compensated design to reduce vibrations, which results in a minimization of eddy currents and acoustic noise. The advanced fully-dynamic parallel transmit radiofrequency (RF) technology in this system integrates all transmit and receive components within the magnet housing, providing industry leading signal-to-noise performance and high image stability with minimal RF noise artifact. The complete system is equipped with a 64-channel phasedarray parallel transmit and receive RF head/neck coil, providing maximal image quality with exceptionally high spatial and temporal resolution for all brain imaging pulse sequences.

The scanner is housed within the Temple University Brain Research and Imaging Center (TUBRIC), a 3400sf, multi-modal, research imaging center serving the neuroimaging research community on Temple's main campus. TUBRIC is a fully functional research-dedicated facility with immediately adjacent participant preparation, testing, and interview space, furnished with a range of integrated and supplemental research instruments to complement basic imaging work. The facility is staffed by a director, a neuroimaging supervisor who has a PhD in Biomedical Engineering, and administrative and IT support personnel. TUBRIC has a standardized certification process to ensure study personnel utilize the scanner and imaging center to maximize subject and personnel safety.

8) Resources Available to Conduct the Human Research INTRODUCTION and rationale

Therapeutic Strategies for Treating Cocaine Use Disorder

Cocaine (COC) related overdose deaths in non-Hispanic black populations are on par with heroin and prescription opioid associated deaths in non-Hispanic white populations (Shiels et al. 2018). Cocaine is a consistent and important contributor to deaths in non-Hispanic white populations and Hispanic populations. Prevention of cocaine-related deaths, which disproportionally affect older non-Hispanic blacks, is urgently needed. A variety of neuropharmacological strategies are being pursued in the search for an effective treatment for Cocaine Use Disorder (CoCUD). These include: 1) blocking cocaine's effects, 2) restoration of central nervous system homeostasis, 3) reducing craving or enhancing the addict's ability to manage his/her response to craving, 4)

treating underlying comorbid conditions that may predispose subpopulations toward dependence, and 5) stress reduction to prevent relapse.

Study Site

This is an inpatient study that will take place at the Episcopal, TUH Main, Jeanes Hospital, and Main campus of Temple University. The first part of the screening visit can be completed in person or over the phone/video. Inpatient sessions are conducted at Centennial 6 at the Episcopal Hospital campus of the Temple University Health System (T-EH). In the event that space is unavailable on C6 for medical reasons, Temple University Hospital Main (TUH-Main) and Jeanes Hospital medical floors which can provide nursing staff who are not currently assigned Covid patients will serve as back up sites. Subject rooms are semi-private (on a unit with other patients) and subjects will be able to complete all study surveys privately.

Blood will be drawn at TUBRIC or on the inpatient unit for all study sessions by staff who are trained and certified to draw blood for research studies. TUBRIC and the inpatient units have a fully equipped blood draw room that will be stocked with all necessary blood draw supplies.

Research Staff Training

[figure not shown]
Training of research study staff will be conducted by Drs. [name], [name] (or TUBRIC staff), [name] and the research specialist. Training will include background on cocaine use disorders, remission and assessing medication adherence in substance abuse populations, information about the rationale for *CLAV*, and information about performing MRS studies safely. TUBRIC staff will conduct training regarding the TUBRIC scanner and subject safety. The training team will ensure that study staff understand and accept the nature of the protocol and the requirements for an adequate, safe and ethical study. Specifically, their obligation to conduct the clinical investigation in accordance with Good Clinical Practices (GCP) and any other regulations will be reinforced. Study conduct training will include protocol review, patient confidentiality, procedures regarding study drug administration, procedures with assessments and urine testing. Procedures for correctly accounting for and disposing of extra study drug will be reviewed. Procedures for assessing and treating adverse events will be discussed.

9) Prior Approvals

The Investigational New Drug (IND) application with the FDA (IND# 113621) was approved in 2015. This protocol will be submitted to the FDA concurrently with the submission to the Temple IRB. CLAV has been approved for Fast Track Designation by the FDA for CocUD.

10) Study Design

This Phase IB study of CLAV will investigate brain regional glutamate levels before and after repeated 10-day CLAV dosing to determine whether glutamate is reduced in the ACC after repeated CLAV dosing in a dose escalating study. The study will be performed with 5 imaging days (5 MRS scans) over 11 inpatient study days in total with three outpatient visits. It will be conducted in subjects with moderate to severe cocaine use disorder in with 1 week or more of abstinence.

Structural MRI, functional

MRI, and MRS will occur before CLAV administration at baseline, after 3 days of study drug administration (prior to 750mg dose escalation), after 6 days of study drug administration (prior to the 1000mg dose escalation) on the last day of CLAV dosing (day 10), and one day after the Cessation of CLAV dosing (day 11). The final MR scan session will be used to gather information on the duration of CLAV's effect on ACC Glu concentration after cessation of CLAV dosing. Before each scan, safety of the subject to complete the scan will be re-assessed. Subjective and cognitive assessments will be administered daily in the inpatient setting. Assessments of adverse effects, blood pressure and pulse will also be performed daily.

The study will end with a follow up visit 5-8 days after discharge. The follow visit will involve an assessment of adverse events to determine withdrawal symptoms. Subjects with adverse events that require further in person assessments may be asked to come in for an additional visit. All adverse events will be followed until resolution.

Informed Consent and Screening Part 1 (Approximately 120 minutes, in- person or over the phone)

In-Person Consent and Screening Procedure

In a private setting, each participant will receive a description by a study staff member of the study protocol, its risks, potential benefits, and alternative treatments available. A study physician will be present and involved in the consent process. A consent quiz will be administered after review of the consent, and prior to when participants sign the consent form. Participants will need to understand the answer to all questions correctly before signing. Participants who answer questions incorrectly will review those questions with research staff, who will explain the sections of the consent form that are

relevant to the incorrect guiz guestions. Following completion of the consent guiz and resolution of any questions, participants who understand the nature of the study and consent will be asked to sign the study consent form, which will also be signed by the physician present. A copy of the informed consent form will be given to each participant and participants will be reminded that the consent expresses willingness to participate but that the subsequent screening process will determine final eligibility. Further, each participant will be reminded that participation is voluntary, and at any time, s/he may withdraw from the study. Following the informed consent process, a research coordinator will perform assessments during the outpatient screening visit including: 1) collection of demographic information, 2) a timeline follow back (TLFB) interview covering the preceding 42 days 3) cocaine use guestionnaire, including reactions to cocaine, history of other substance use (including cigarettes), number of prior cocaine quit attempts and reasons for relapse. A trained coordinator or clinician will perform the MINI, a psychiatric diagnostic interview Vital signs will be collected. A study physician will take a medical history including drug allergies and medications. 4) Participants who are potentially eligible at this stage of the screening will be provided transport to the Temple Health Sciences campus to receive a Covid-19 test. Participants who test negative will be scheduled for the second half of the screening visit.

Phone Consent and Screening Procedures

Participants who complete the first part of the screen over the phone will review the consent with a study physician and complete a consent quiz. After completion of the consent quiz, participants will be provided a RedCAP link which will allow them to virtually sign the consent form. Participants who sign the consent form virtually will complete the same assessments as individuals who complete the screening visit 1 in person. At the end of the part 1 screening visit participants will be sent a copy of the consent form by e-mail or mail.

Participants who are interested in the study but do not have internet access to complete the form can be sent a preaddressed and stamped envelope with a blank consent form, which they can return to the research team. The screening visit will be completed at a later date when the signed form is received.

If a participant is determined to be eligible for the research study, they will be scheduled for a Covid-19 test on the Temple Health sciences campus. Participants who test negative will be scheduled for the second half of the screening visit.

Screening Part 2 (Approximately 90 minutes, in- person)

Participants have up to 90 days after the completion of screening part 1 to complete screening part 2. Participants who attend screening part 2 more than 30 days after screening part 1 will update their medication history, medical history and recent substance use information.

Upon arrival for the part 2 visit, participants will be asked to show legal picture identification. Participants who completed the first part of the screen virtually will be asked to sign a physical copy of the informed consent and will be provided a copy. A physician will perform a physical exam. Laboratory assessments (blood & urine) will be checked including a comprehensive metabolic panel, CBC, infectious disease panel, including human immunodeficiency virus (HIV) type 1 and 2, and urine tests for drugs of abuse, pregnancy (women) and urinalysis. Approximately 15ml (1 tablespoon) of blood will be collected at this visit. A breathalyzer test will be completed. An EKG will be performed and reviewed.

If a participant can be scheduled for admission within 96 hours, they will be provided transport to the Temple Health Sciences campus to receive a Covid-19 test. If participants cannot be scheduled for admission within 96 hours at the time of the screening part 2 visit, they will be scheduled for a test within 96 hours prior to their admission date.

Participants can receive up to 2 additional Covid-19 tests (4 total) as needed to account for unanticipated scheduling changes, and increase scheduling flexibility for admission.

Table 1. Study Assessments												
	Screenin g visit 1 (-30 to 0 days)	Screening Visit 2 (-30 to 0 days)	Day 1 Baseline	Day 2	Day 3	Day 4	Days 5	Day 6	Days 7-9	Day 10	Day 11	Follow Up (Day 16 - 19)
ICF with HIPAA	Х											
Cocaine Use Questionnaire	Х											
Illicit Drug Use TLFB (preceding 30 days or less on follow up)	х		х									х
Medical record review	Х											
Demographics	Х											
Vital signs	X1	Х	Х	Х	Х	Х	Х	Х	Х	Х	Х	Х
Medical History	Х											
Nasopharyngeal swab (Covid-19 test)	х	Х										
Physical Exam		Х										
Labs (CBC, Metabolic Panel)		Х			Х			Х		Х		
Labs (Hepatitis B, C, HIV)		Х										
EKG		Х								Х		
